NON-INTERVENTIONAL POST-AUTHORIZATION SAFETY STUDY PROTOCOL

Study Title	A Prospective, Longitudinal, Observational Registry of Truvada for HIV-1 Pre-Exposure Prophylaxis (PrEP) of Adults and Adolescents in Europe
Protocol ID	GS-EU-276-4487
Protocol Version/Date:	1.0 21 March 2018 1.1 17 August 2018 1.2 28 March 2019 1.3 20 August 2019 1.4 20 January 2020
EU PAS Register No	To be registered
Active Substance	Emtricitabine/tenofovir disoproxil fumarate (FTC/TDF) 200 mg/245 mg film-coated tablets
Medicinal Product	Truvada [®]
Product Reference	EU/1/04/305/001 EU/1/04/305/002
Procedure Number	NA
Joint PASS	No
Research Question and Objectives	The objectives of this registry are to: (1) Describe how Truvada for PrEP is prescribed or self-initiated, including the dosing pattern (dose and schedule as daily/intermittent); (2) Characterize the demographics of adults and adolescents who were prescribed or are taking Truvada for PrEP and their HIV risk factors; (3) Characterize the nature and frequency of individual monitoring after initiating Truvada for PrEP, including any available information on adherence; (4) Document any cases of new HIV diagnoses and development of any resistance to Truvada, and selected safety data; and (5) Summarize the characteristics of healthcare professionals who prescribe Truvada for PrEP.
Countries of Study	Belgium, France, Norway, Portugal, and Sweden
Gilead Study Director / Author / Contact Person	Name: PPD Telephone: PPD
Marketing Authorization Holder	PPD
MAH Contact Person	Name: PPD Telephone: PPD

**Gilead Qualified
Person Responsible for
Pharmacovigilance**

Name:
Telephone:

PPD
PPD

CONFIDENTIALITY STATEMENT

The information contained in this document, particularly unpublished data, is the property or under control of Gilead Sciences, and is provided to you in confidence for review by you, your staff, and an applicable Independent Ethics Committee. The information is only to be used by you. You will not disclose any of the information to others without written authorization from Gilead Sciences, except to the extent necessary to obtain informed consent from those persons who will participate in the study.

2. GLOSSARY OF ABBREVIATIONS AND DEFINITION OF TERMS

AE	adverse event
ADR	adverse drug reaction
CRO	contract research organization
DP	diphosphate
eCRF	electronic case report form
EDC	electronic data capture
eGFR	estimated glomerular filtration rate
EU	European Union
F	female
FTC	emtricitabine
GPP	Good Pharmacoepidemiology Practices (guidelines for)
Gilead	Gilead Sciences/Gilead Sciences, Inc.
GVP	Good Pharmacovigilance Practices
HBV	hepatitis B Virus
HCP	Healthcare Professional
HCV	hepatitis C Virus
HIV-1	Human Immunodeficiency Virus Type 1
HMA	Heads of Medicines Agencies
ICH	International Council for Harmonisation (of Technical requirements for Pharmaceuticals for Human Use)
IEC	independent ethics committee
M	male
MSM	men who have sex with men
PAS	post-authorization study
PASS	post-authorization safety study
PrEP	pre-exposure prophylaxis
PEP	post-exposure prophylaxis
PRAC	Pharmacovigilance Risk Assessment Committee
PVE	Pharmacovigilance and Epidemiology. A department at Gilead Sciences that was renamed to Pharmacovigilance and Epidemiology (PVE), effective 01 December 2017.
SADR	serious adverse drug reaction
SAE	serious adverse event
SmPC	summary of product characteristics
TDF	tenofovir disoproxil fumarate

4. PROTOCOL SYNOPSIS/ABSTRACT

Gilead Sciences, Inc.
[name]
[name]

Title: A Prospective, Longitudinal, Observational Registry of Truvada for HIV-1 Pre-Exposure Prophylaxis (PrEP) of Adults and Adolescents in Europe

Rationale and Background: A European Commission Decision was received on 18 August 2016 for a Type II Variation for Truvada® (emtricitabine/tenofovir disoproxil fumarate; FTC/TDF) to extend the indication to include PrEP in combination with safer sex practices to reduce the risk of sexually acquired HIV-1 infection in adults at high risk. A subsequent European Commission Decision was adopted on 05 February 2018 for a Type II Variation to expand the indication for PrEP to adolescents weighing at least 35 kg, in accordance with the agreed pediatric investigation plan for Truvada.

The Truvada summary of product characteristics (SmPC) states that Truvada is indicated in combination with safer sex practices for PrEP to reduce the risk of sexually acquired HIV-1 infection in adults and adolescents at high risk.

This registry is designed to collect real-world data on use of Truvada for PrEP in adults and adolescents in Europe.

Research Question and Objectives: The objectives of this voluntary participation registry are as follows:

- 1) To describe how Truvada for PrEP is prescribed or self-initiated, including the dosing pattern (dose and schedule as daily/intermittent)
- 2) To characterize the demographics of adults and adolescents who were prescribed or are taking Truvada for PrEP and their HIV risk factors
- 3) To characterize the nature and frequency of individual monitoring after initiating Truvada for PrEP, including any available information on adherence
- 4) To document any cases of new HIV diagnoses and development of any resistance to Truvada, and selected safety data
- 5) To summarize the characteristics of healthcare professionals who prescribe Truvada for PrEP

Study Design: This will be a prospective, longitudinal, observational, and voluntary participation registry of the real-world usage of Truvada

for PrEP to prevent HIV-1 infection in adults and adolescents in Europe. Due to the restricted availability of Truvada for PrEP in various European countries, this registry will initially be conducted in a limited number of European countries where Truvada for PrEP is being reimbursed. Initially, the target countries to be included in the registry will be Belgium, France, Norway, Portugal, and Sweden. Other countries may be included following reimbursement approval of Truvada for PrEP. Within each of the countries where drug utilization will be assessed, representative healthcare institutions (where biomedical interventions for HIV prevention are being prescribed) and institutions with individuals who have discontinued participation in clinical studies or demonstration projects with Truvada for PrEP will be assessed for feasibility to participate in this registry which will focus on all individuals receiving Truvada for PrEP. This registry will not provide Truvada.

Both male and female adults and adolescents will be recruited for enrollment in the registry. Individuals who started Truvada for PrEP prior to first presenting to the participating healthcare professional (HCP) or are prescribed Truvada for PrEP will be eligible for enrollment. Individuals receiving Truvada for PrEP will be followed and relevant demographic and ongoing use data will be collected in the registry. The individuals who agree to participate in the registry will receive treatment solely based on current clinical practice in the country in which they reside. The use of Truvada for PrEP should be within the conditions of its approved SmPC. However, Gilead will not influence decision making by the participating HCPs or restrict enrollment into the registry to those individuals who are not receiving drug in full compliance with the SmPC (where local regulations allow to do so) as the objective of the registry is to describe the patterns of use and monitoring in real life. Data on intermittent use of Truvada for PrEP will be collected in countries permitting such data collection. The frequency of clinic visits will be at the discretion of the prescriber.

Details on the product prescribed, the healthcare institution characteristics, and prescriber characteristics will also be collected.

Country-specific protocols may be developed to comply with local regulations on data collection. Gilead will work with a contract research organization to develop and launch the registry.

Population:

Both adults (≥ 18 years of age) and adolescents weighing at least 35 kg (eg, 12 to 17 years of age) receiving Truvada for PrEP will be included as the primary population for this registry. Furthermore, the registry will collect data on HCPs who prescribe Truvada for PrEP.

Inclusion criteria:

- HIV-1 negative adults and adolescents who are deemed to be at high risk for acquiring HIV-1
- HIV-1 negative adults and adolescents who provide consent / assent and, depending on local country regulations, parental or legal guardian permission to participate in the registry
- HIV-1 negative adults and adolescents who are receiving Truvada for HIV PrEP, either as a daily or intermittent regimen, and that are clinically monitored

Exclusion criteria:

- Individuals currently participating in a clinical study of HIV PrEP

Variables: Individual data elements will be collected as available after enrollment and while participating in the registry. Data will include: age, gender at enrollment, weight and height, HIV risk factors, concurrent sexually transmitted infections, hepatitis B virus serostatus, hepatitis C virus serostatus, prior PrEP or post-exposure prophylaxis use, estimated glomerular filtration rate, serum phosphate, use of recreational drugs during sex, and PrEP adherence assessment. Pregnancy status will be requested for females. PrEP prescription/usage details will include: dose schedule, initiation (ie, prescription or self-initiation) date and stop date or duration of PrEP usage, and the tablet and refill quantity. If seroconversion occurs, additional data include date of seroconversion, circumstances of HIV acquisition if available, and results of HIV-1 resistance testing if available. Selected safety data for collection in the registry will include all fatal events, serious adverse drug reactions (SADRs), treatment-related renal or bone adverse drug reactions, and pregnancy reports. Possible factors leading to new HIV infection, genotypic resistance testing, and reason for PrEP discontinuation will also be collected.

Details on the participating institutions will include location and type of institution. HCP data will include provider specialty and if they routinely treat individuals with HIV-1 infection.

Data Sources: Prescriber information will be collected at enrollment. Available clinical and laboratory data will be collected by HCPs from medical records at treatment initiation and at follow-up time points (eg, initiation of PrEP, clinic visits, discontinuation of PrEP, and at time of HIV-1 seroconversion if applicable).

Study Size: The purpose of the registry is to provide insight into the patterns of Truvada for PrEP usage and how clinicians are monitoring individuals on Truvada for PrEP. The registry is not designed or powered to compare rates of seroconversion or adherence with studies or demonstration projects.

Enrollment will be open to both adults and adolescents and individuals will be followed while Truvada for PrEP is continued. Target is to enroll and follow enough adults to provide at least 400 person-years of follow-up data and enough adolescents to provide at least 25 person-years of follow-up data.

Data Analysis: Descriptive analyses will be used to summarize the available data. There are no statistical hypotheses to evaluate. Categorical variables will be reported by proportions and continuous variables will be reported by mean, standard deviation, minimum, median, and maximum. Prescriber characteristics will be summarized.

Demographics and clinical characteristics of individuals on Truvada for PrEP will be analyzed. The products prescribed and available prescription details including duration of PrEP, the frequency of monitoring, any relevant data on adherence monitoring, and reported safety events (fatal events, SADRs, renal or bone ADRs) will be summarized. Seroconversion cases and results of resistance testing will be summarized. Reported pregnancies will also be analyzed.

Rates of adherence and new HIV diagnoses (ie, seroconversion) will be calculated with 95% confidence intervals. Results will be presented overall and by subgroups including adults and adolescents, gender, and country.

Milestones:

Start of data collection: Target start date of data collection is end of Q4 2020 (after Pharmacovigilance Risk Assessment Committee [PRAC] approval of the protocol).

End of Data collection: Enrollment will be open for 3 years after the first individual enrolls. Data collection will continue for 6 months after the 3-year enrollment period, estimated to be completed by Q2 2024.

Interim report: Interim reports will be prepared annually after opening enrollment, estimated for Q4 in 2021 and 2022.

Final report: A final report will be submitted within 12 months of end of data collection, estimated for release before Q2 2025.

This registry will be conducted in accordance with the guidelines of Good Pharmacoepidemiology Practices (GPPs) and Heads of Medicines Agencies (HMA) Good Pharmacovigilance Practices (GVP) including archiving of essential documents.

5. AMENDMENTS AND UPDATES

Table 5-1. Protocol Amendments and Updates

Amendment or Update Number	Date	Section of Study Protocol	Amendment or Update	Reason
Version 1.1	17 August 2018	Entire protocol	Update	Protocol revised based on comments from the PRAC. Due to the data gap regarding use of HIV PrEP in adolescents and young adults, the registry was revised to focus enrollment and data collection on adolescents and young adults
Version 1.2	28 March 2019	Entire protocol	Update	Protocol revised based on discussions with the PRAC to develop a survey of healthcare professionals to capture data on PrEP usage across the EU
Version 1.3	20 August 2019	Entire protocol	Update	Protocol revised based on discussions with the PRAC to develop a registry for both adults and adolescents taking PrEP
Version 1.4	20 January 2020	Entire protocol	Update	Protocol revised based on comments provided from the PRAC including removal of reference to generic FTC/TDF

PRAC Pharmacovigilance Risk Assessment Committee

5.1. Protocol Modifications

Protocol modifications may be made only by Gilead Sciences.

6. MILESTONES

Table 6-1. Registry Milestones

Milestone	Planned Date
Start of data collection	The registry will be opened for recruitment in each of the selected countries after approval/notification by the relevant National Competent Authority and Ethics Committee as required. Target start date of data collection is end of Q4 2020.
Enrollment period	3 years (Q4 2020 until Q4 2023)
End of data collection	6 months after enrollment of the last individual (Q2 2024)
Interim report 1	1 year after first enrollment (Q4 2021)
Interim report 2	2 years after first enrollment (Q4 2022)
Registration in the EU PAS register	Prior to Start of Enrolment (Q4 2020)
Final report of study results	A final report will be submitted within 12 months of end of data collection (Prior to Q2 2025)

7. RATIONALE AND BACKGROUND

7.1. Rationale for the Current Study

A European Commission Decision was received on 18 August 2016 for a Type II Variation for Truvada® (emtricitabine/tenofovir disoproxil fumarate; FTC/TDF) to extend the indication for pre-exposure prophylaxis (PrEP) in combination with safer sex practices to reduce the risk of sexually acquired HIV-1 infection in adults at high risk. A subsequent European Commission Decision was adopted on 05 February 2018 for a Type II Variation to expand the indication for PrEP to adolescents weighing at least 35 kg, in accordance with the agreed pediatric investigation plan for Truvada.

The Truvada summary of product characteristics (SmPC) states that Truvada is indicated in combination with safer sex practices for PrEP to reduce the risk of sexually acquired HIV-1 infection in adults and adolescents at high risk.

The incidence of HIV infections in the European Union (EU) and European Economic Area for 2017 is estimated at 6.2 per 100,000 people {[World Health Organization \(WHO\) 2018a](#)}. The rates per country varied across countries, including 4.4 per 100,000 people in Sweden, 6.7 per 100,000 people in the United Kingdom, 7.9 per 100,000 people in Belgium, 8.2 per 100,000 people in France, and 14.2 per 100,000 people in Portugal. Males who have sex with males accounted for 38.2% of cases of new HIV infections.

The safety and efficacy of once daily oral Truvada in the prevention of HIV-1 acquisition among men who have sex with men (MSM) have been demonstrated in a large (n = 2499), multinational, randomized, placebo-controlled, double-blind, Phase 3 study (also known as the PrEP Initiative [iPrEx] study [CO-US-104-0288]) {[Grant et al 2010](#)}. The safety and efficacy of once daily oral Viread® (tenofovir disoproxil fumarate) or Truvada in the prevention of HIV-1 acquisition among East African heterosexual men and women in 4747 HIV-1 serodiscordant partnerships were demonstrated in a randomized, placebo-controlled, double-blind, Phase 3 study (also known as the Partners PrEP study) {[Baeten et al 2012](#)}.

The WHO Implementation Tool for Pre-Exposure Prophylaxis (PrEP) of HIV Infection, Module 12 Adolescents and Young Adults (released July 2018) identifies adolescents and young adults as a high risk group for acquiring HIV and accounts for 37% of the new HIV infections {[World Health Organization \(WHO\) 2018b](#)}.

Safety, adherence, and resistance were evaluated in a single-arm, open-label clinical trial (ATN113) in which 67 HIV-1 uninfected adolescent MSM received Truvada once daily for PrEP {[Hosek et al 2017](#)}. The mean age of subjects was 17 years (range 15 to 18 years); 46% were Hispanic, 52% black, and 37% white. No new adverse drug reactions (ADRs) were identified in Study ATN113.

In Study ATN113, no seroconversions occurred in any subject who had tenofovir diphosphate (TFV-DP) levels associated with protection against rectal HIV exposure. HIV seroconversion occurred in 3 subjects: 2 subjects with TFV-DP levels below the limit of quantitation and 1 subject with TFV-DP levels that correlate with < 2 doses per week on average (< 350 fmol/sample). No tenofovir- or emtricitabine-associated HIV-1 resistance mutations were detected in the 3 seroconverters. The incidence rate for new HIV infections (seroconversion) is 6.4% (6.4 per 100 person-years). Adherence in adolescents in Study ATN 113 was assessed by dried blood spot, which demonstrated that 55% of adolescents 15 to 17 years of age at Week 12 had dried blood spot TFV concentrations of > 700 fmol/punch, consistent with taking at least 4 Truvada tablets per week.

The Amsterdam PrEP demonstration project reported that in 269 adults (≥ 18 years) taking Truvada for PrEP on a daily basis and followed for up to 2 years, the incidence rate for new HIV infections (seroconversion) is 0.4% (0.4 per 100 person-years) {[Hoorneborg et al 2019](#)}.

Data on the use of Truvada for PrEP in adults have been generated from controlled clinical studies and more recently in observational studies and PrEP demonstration projects. Data on the use in adolescents and young adults are however limited. This registry is designed to collect real-world data on use of Truvada for PrEP in adults and adolescents in Europe.

7.2 Rationale for differences to Non-Interventional Study Design Requirements This registry will have a focused safety data collection approach, as specified below, to meet the key objectives of the registry without adding additional overhead data collection with limited scientific value for the purposes of the registry. Gilead has requested a waiver from standard collection of AEs for this noninterventional post-authorization safety study (PASS), which was agreed upon by PRAC

Per Good Pharmacovigilance Practices (GVP) Module VIII, noninterventional PASS should use the medicinal product in accordance with the terms of the marketing authorization. Truvada for PrEP is approved for daily administration. However, in order to meet the objectives of interest to the PRAC, it will be critical not to limit data collection only to individuals who are prescribed a continuous regimen as per SmPC, but accept all individuals on any dosing regimen (where local regulations allow to do so) in order to maximize the opportunity to gather important knowledge of the true PrEP usage patterns. Limiting collection of data to be consistent with terms of marketing authorization will exclude the proportion of PrEP users who are prescribed PrEP with other dosing regimens and not provide a full description of PrEP usage. Despite this fact, the registry will retain a noninterventional classification, as the impact of a clinical study on the behavior of both prescribers and participants would be in direct contrast to the main objective of this undertaking to observe the real-life use of Truvada. Country-specific protocols may be developed to comply with local regulations on data collection.

Further and in difference to GVP Module VI collection, management and submission of reports of suspected adverse reactions to medicinal products (revision 2) as specific to commercial sponsors, this protocol proposes to collect only a reduced set of selected safety data. Truvada has been marketed since 2004 and has accumulated over 4 million patient-years of

experience (predominantly in HIV-1 infection). The safety profile is well characterized in clinical studies and through extensive monitoring of post-authorization use. This registry is primarily focused on establishing patterns of use. Collecting all adverse events (AEs) may be of little scientific value and it is feared that the burden of extensive data collection may adversely affect recruitment of both prescribers and participants. This registry will collect selected safety information, ie, fatal events, all serious ADRs, treatment-related bone or renal ADRs, and pregnancies.

8. RESEARCH QUESTIONS AND OBJECTIVES

The objectives of this registry are as follows:

- To describe how Truvada for PrEP is prescribed or self-initiated, including the dosing pattern (dose and schedule as daily/intermittent)
- To characterize the demographics of adults and adolescents who are receiving Truvada for PrEP and their HIV risk factors
- To characterize the nature and frequency of individual monitoring after initiating Truvada for PrEP, including any available information on adherence
- To document any cases of new HIV diagnoses and development of any resistance to Truvada and selected safety data
- To summarize the characteristics of healthcare professionals who prescribe Truvada for PrEP

9. RESEARCH METHODS

9.1. Study Design

This is a prospective, longitudinal, observational, and voluntary participation registry designed to characterize the real-world use of Truvada for PrEP to prevent HIV-1 infections in adults and adolescents in Europe. The individuals who agree to participate in the registry will receive treatment solely based on current clinical practice in the country in which they reside. The use of Truvada for PrEP should be within the conditions of its approved SmPC. However, Gilead will not influence decision making by the participating HCPs or restrict enrollment into the registry to those individuals who are not receiving drug in full compliance with the SmPC (where local regulations allow to do so) as the objective of the registry is to describe the patterns of use and monitoring in real life. Data on intermittent use of Truvada for PrEP will be collected in countries permitting such data collection.

Both male and female adults and adolescents will be recruited for enrollment in the registry. Individuals who started Truvada for PrEP prior to first presenting to the participating HCP or are prescribed Truvada for PrEP will be eligible for enrollment. Baseline will be considered as the start date of Truvada for PrEP. The data for individuals receiving Truvada for PrEP prior to enrollment will be collected retrospectively from the individual's medical record.

Individuals will be followed while on Truvada for PrEP and the frequency of clinic visits will be at the discretion of the prescribers. Individuals will be followed until they are either lost to follow up, discontinued Truvada for PrEP, become infected with HIV, withdraw consent, or registry closure.

Details on Truvada for PrEP use, the healthcare Institution characteristics, and prescriber characteristics will also be collected .

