Recruitment methods within each country will begin by assessing if they have a national policy for PrEP or a similar initiative that would support reimbursement of all HIV-1 PrEP medicinal products or only Truvada or generic equivalents products. HCPs who prescribe products for HIV-1 PrEP will be contacted to determine if they prescribe Truvada for PrEP and if so they will be invited to participate in the registry. Additionally, a review of planned, ongoing, or completed clinical studies or demonstration projects which include Truvada for PrEP will be carried out to identify potential individuals who have completed or discontinued participation in the study but continue to take Truvada for PrEP.

A written contract on the implementation of this registry shall be concluded between sponsor and clinical site. Personnel from the sponsor company or the contract research organization (CRO) will describe the registry to HCPs at each site and provide training on the registry design and data collection to ensure, as much as possible, quality and consistency of data collected. HCPs will only be compensated for their time and efforts on the registry based on current fair market value at the time of contract finalization.

9.2.1. Inclusion Criteria:

- HIV-1 negative adults and adolescents who are deemed to be at high risk for acquiring HIV-1
- HIV-1 negative adults and adolescents who provided consent / assent and, depending on local country regulations, parental or legal guardian permission to participate in the registry
- HIV-1 negative adults and adolescents who are receiving Truvada for HIV PrEP, either as a daily or intermittent regimen, and that are clinically monitored

9.2.2. Exclusion Criteria:

- Individuals currently participating in a clinical study of HIV PrEP

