9.3.1. Exposure

Data on Truvada for PrEP will be collected. The start and stop dates will be used to estimate person-time of exposure to Truvada. Person-time of exposure will be defined as ([PrEP end date - PrEP initiation date] + 1), regardless of temporary interruptions in exposure (< 30 days) and will be expressed in days (recorded in whole days, eg, 41 days). Exposure starts the first day the medication was prescribed or self-initiated (and assumed to have been taken). An individual may have multiple exposures defined as the re-initiation of PrEP after a period of stoppage that is greater than 30 days. Aggregated person-time may also be expressed in person-years ([number of person days]/365.25). Individuals who are taking PrEP on an intermittent or event-driven basis will have exposure calculated in a similar fashion ([PrEP end date - PrEP initiation date] + 1).

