9.5. Study Size

The purpose of the registry is to provide insight into the patterns of Truvada for PrEP usage and how clinicians are monitoring individuals on Truvada for PrEP. The registry is not designed or powered to compare rates of seroconversion or adherence with studies or demonstration projects.

Enrollment will be open to both adults and adolescents, and enrolled individuals will be followed while Truvada for PrEP is continued. Target is to enroll and follow enough adults to provide at least 400 person-years of follow-up data and enough adolescents to provide at least 25 person-years of follow-up data.

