9.7. Data Analysis

Descriptive data analysis will be used to summarize the available data. There are no statistical hypotheses to evaluate. Categorical variables will be reported by proportions and continuous variables will be reported by mean, standard deviation, minimum, median, and maximum. Prescriber characteristics will be summarized. Demographics and clinical characteristics of individuals on Truvada for PrEP will be analyzed. The products prescribed and available prescription details, the frequency of monitoring, and any relevant data on adherence monitoring will be summarized. Seroconversion cases and results of resistance testing will be summarized. Reports of treatment-related renal and bone adverse drug reactions (SADRs and ADRs) will be summarized. Females participants in the registry who are pregnant will also be analyzed.

Data will be presented overall, and by age group (adolescents and young adults) and risk factors for HIV transmission.

Rates of adherence and new HIV diagnoses (i.e., seroconversion) will be calculated with 95% confidence intervals. Results will be presented overall and by subgroups including adults and adolescents, gender, and country.

Comprehensive information relating to the analysis of this registry will be provided in the statistical analysis plan.

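### Person-time starts at PrEP initiation although existing users must be HIV-negative at a later enrolment; used as the denominator of the seroconversion rate, it biases that rate low

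*Protocol*

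**What the plan says.** - **Time origin (Protocol 9.1).** People who started Truvada before presenting to the participating prescriber are eligible. Their earlier data are taken retrospectively from the medical record, and "Baseline will be considered as the start date of Truvada for PrEP".
- **Person-time (Protocol 9.3.1).** "Person-time of exposure will be defined as ([PrEP end date - PrEP initiation date] + 1" day, and "Exposure starts the first day the medication was prescribed or self-initiated". No other person-time definition appears.
- **Entry (Protocol 9.2 and 9.2.1).** Users are assessed when they attend a routine visit. Those who enter must be "HIV-1 negative adults and adolescents who are receiving Truvada for HIV PrEP". Section 9.2 also plans to look for people who have left PrEP studies or demonstration projects and still take Truvada.
- **Rate (Protocol 9.7).** "Rates of adherence and new HIV diagnoses (i.e., seroconversion) will be calculated with 95% confidence intervals". The denominator is not named.
- **Size (Protocol 9.5).** Adults are to provide "at least 400 person-years of follow-up data"; adolescents at least 25.

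No section separates time before enrolment from time after it. The limitations in section 9.9 cover selection, representativeness, data quality and adolescent recruitment, but not this.

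**The concern.** For someone who starts Truvada on the day of enrolment, the two clocks coincide and nothing is wrong. For an existing user they do not. That person is in the registry only because no HIV infection occurred between PrEP start and the enrolling visit. A similar user who was infected in that span fails the HIV-negative criterion and is never counted. The span is therefore immortal with respect to seroconversion: it lengthens the denominator and cannot contribute to the numerator. This is left truncation without delayed entry, and the error can go in one direction only, towards a lower reported rate.

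Existing users are not incidental here. The search among former study and demonstration-project participants may bring in people with long prior use, each with a long event-free span.

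What is at stake is one of the two quantities for which section 9.7 promises confidence intervals. With few events expected, the upper limit is likely to be what readers take from the result, and it would look more reassuring than the data allow.

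**Working it through.** **Inputs from the protocol.** Targets of 400 and 25 person-years (PY) (9.5). Background rates of 0.4 per 100 PY in adults and 6.4 per 100 PY in adolescents (7.1), used only for illustration. The targets come with no derivation, so there is no planned figure to reproduce.

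**Inputs assumed.** The documents do not give the share already on PrEP (p), their mean prior use in years (L), or mean follow-up after enrolment in years (F). A constant hazard is assumed, and the same mean F for new and existing users.

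**Bias factor.** Per person, at-risk time is F and counted time is F + pL, while the events are the same. So

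reported rate / true rate = F / (F + pL) = 1 − f, where f = pL / (F + pL) is the pre-enrolment share of person-time.

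| p | L | F | F + pL | Factor |
|---|---|---|---|---|
| 0.25 | 0.5 | 1.5 | 1.625 | 0.92 |
| 0.50 | 1 | 1.5 | 2.0 | 0.75 |
| 0.50 | 2 | 1.5 | 2.5 | 0.60 |
| 0.75 | 2 | 1.0 | 2.5 | 0.40 |

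**Effect at the stated person-years, if they include pre-enrolment time.** Expected events are true rate × PY × (1 − f); the reported rate divides these by all PY.

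| f | Adults, 400 PY: events | Reported per 100 PY (true 0.4) | Adolescents, 25 PY: events | Reported per 100 PY (true 6.4) |
|---|---|---|---|---|
| 0 | 1.6 | 0.40 | 1.6 | 6.4 |
| 0.10 | 1.44 | 0.36 | 1.44 | 5.76 |
| 0.25 | 1.2 | 0.30 | 1.2 | 4.8 |
| 0.50 | 0.8 | 0.20 | 0.8 | 3.2 |
| 0.75 | 0.4 | 0.10 | 0.4 | 1.6 |

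**Confidence limits.** With zero events the exact Poisson 95% upper limit is 3.689 / PY, and the lower limit is 0 either way.

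- On 400 PY: 3.689 / 400 = 0.92 per 100 PY.
- With p = 0.5, L = 1, F = 1, the factor is 1 / 1.5 = 0.667, so 400 counted PY hold 267 at risk: 3.689 / 267 = 1.38 per 100 PY.

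With two events on 400 PY the reported result is 0.50 (0.06 to 1.81) per 100 PY. If the factor is 0.75, dividing by it gives 0.67 (0.08 to 2.41).

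**Simulation check.** Everyone is an existing user. Infection hazard is constant; time to stopping PrEP is exponential with mean 2 years; the lag from PrEP start to enrolment is exponential; closure falls uniformly 0.5 to 3.5 years after enrolment. Entry requires being uninfected and still on PrEP at enrolment.

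| True rate per 100 PY | Mean lag (years) | Pre-enrolment share | Rate from PrEP start | Rate from enrolment |
|---|---|---|---|---|
| 0.4 | 0.5 | 25% | 0.30 | 0.41 |
| 0.4 | 1 | 36% | 0.26 | 0.40 |
| 0.4 | 2 | 46% | 0.22 | 0.40 |
| 6.4 | 0.5 | 26% | 4.76 | 6.40 |
| 6.4 | 1 | 36% | 4.09 | 6.40 |
| 6.4 | 2 | 45% | 3.49 | 6.40 |

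Counting from enrolment recovers the true rate; counting from PrEP start does not.

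**The case against.** The strongest reply is that the denominator is inferred. Section 9.3.1 defines exposure, a drug-use quantity. Section 9.7 neither cites it nor names another, and refers to a statistical analysis plan that is not at hand and could start at-risk time at enrolment. The protocol does not use one clock for everything either: section 11.1.1 collects safety information from consent. This stands, and it makes the point conditional. It does not remove it, because the protocol fixes a baseline and supplies one person-time rule; an analysis plan that chose enrolment would be departing from 9.1 and 9.3.1 without support in the protocol.

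A second reply is that the registry is descriptive. Section 9.7 says there is no hypothesis, section 9.5 disclaims power to compare seroconversion rates with other studies, and the objective is to document cases. At 0.4 per 100 PY, 400 PY yields about 1.6 events, and the interval from two events (0.06 to 1.81) is far wider than a shift by a factor of 0.92 or 0.75. This lowers the priority. It does not justify a systematic error, since a published rate should still be divided by time at risk.

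A third reply is that the size rests on assumed inputs. That is correct: the direction is settled whenever existing users enrol and this clock is used, but the size is not known.

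**Conclusion.** The point holds in conditional form. If the person-time of section 9.3.1 is the denominator of the seroconversion rate, pre-enrolment time of existing users is immortal, and the rate and its confidence limits are scaled by F/(F+pL). Under the assumed inputs the factor runs from about 0.92, which is minor, to 0.40, which is not. It is 1 if everyone enrols on the day PrEP starts. It should be fixed, but it does not undermine a descriptive registry that expects few events.

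A reader might infer more than the documents support:

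- *That the rate will certainly be wrong.* Section 9.7 names no denominator.
- *That the synopsis contradicts section 9.1.* It says "Individual data elements will be collected as available after enrollment and while participating in the registry". That concerns when data are gathered; section 9.1 concerns the period they cover. Section 9.2 requires consent before any data collection, so retrospective abstraction also takes place after enrolment.
- *That time after the last HIV test is the same defect.* That would be incomplete ascertainment of the outcome, not time made event-free by an entry condition, and the factor above does not describe it.
- *That prior use alone could meet the 400 person-year target at enrolment.* Section 9.5 speaks of enrolling and following people, which most naturally means time after enrolment. A confirming sentence is enough.

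**What to change.** - **9.3.1:** keep PrEP start-to-stop person-time, labelled as the measure for describing use.
- **9.7:** state that at-risk time for the HIV rate starts at enrolment (the consent date), that is, with delayed entry for existing users, and that pre-enrolment exposure is reported separately.
- **9.5:** confirm that the 400 and 25 person-years are time after enrolment.

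The cost is a few sentences. Informed consent and PrEP start and stop dates are already in Table 9-1, so no new data item is needed. The downside is fewer reported person-years for the HIV rate and wider intervals. Delayed entry removes the bias fully under a constant hazard. If risk is higher soon after starting PrEP, existing users who enrol may still show a lower rate than new starters, and the report should say so.
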